- The date of drug discontinuation, defined as the date of the last continuous treatment episode of the index drug (Montelukast and Fluticasone) plus a defined grace period (i.e., 90 days after the end of the last prescription's days' supply in main analyses).

For analysis 2, the follow-up will start 180 days after initiation of Montelukast and Fluticasone and will continue until the earliest date of the following events:

- The first occurrence of the outcome of interest, unless otherwise specified for selected outcomes,
- The date of end of continuous registration in the database,
- End of the study period,
- Measured death event occurs,
- Maximum allowed follow-up time (1095 days) reached

7. Propensity score analysis

We will use a propensity-score (PS)¹-based approach to account for measured confounding in this study. The PS will be calculated as the predicted probability of initiating the exposure of interest (i.e., the repurposing candidate) versus the reference drug conditional on baseline covariates using multivariable logistic regression constructed separately in each data source. On average, patients with similar PSs have similar distribution of potential confounders used to estimate the PS. Therefore, analyses conditioned on the PS provide effect estimates that are free from measured confounding. For all our analyses, initiators of each exposure of interest will be matched with initiators of the reference exposure based on their PS within each data source.² Pair matching will be conducted using a nearest-neighbor algorithm, which seeks to minimize the distance between propensity scores in each pair of treated and reference patients,³ and a caliper of 0.025 on the natural scale of the PS will be used to ensure similarity between the matched patients.⁴

We report multiple diagnostics for PS analysis in this protocol. First, the PS distributional overlap is provided between two groups before and after matching to ensure comparability of these groups.⁵ Next, balance in each individual covariate between two treatment groups is reported using standardized differences.⁶

8. Table for covariate balance

Variable	Unmatched			PS-Matched		
	Montelukast (N = 12,575)	Fluticasone (N = 38,958)	St. Diff	Montelukast (N = 12,572)	Fluticasone (N = 12,572)	St. Diff
Demographics						
Age, mean (SD)	72.8 (6.1)	73.3 (6.4)	-8.20	72.8 (6.1)	72.8 (6.1)	-0.30
Gender, n (%)						
Male	3694 (29.4)	12706 (32.6)	-7.00	3694 (29.4)	3764 (29.9)	-1.20

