Sarcoidosis, n (%)	60 (0.5)	259 (0.7)	-2.50	60 (0.5)	68 (0.5)	-0.90
Tuberculosis, n (%)	2157 (17.2)	7552 (19.4)	-5.80	2155 (17.1)	2177 (17.3)	-0.50
Acute Upper/ Lower Respiratory Tract infection, n (%)	4789 (38.1)	14315 (36.7)	2.80	4788 (38.1)	4850 (38.6)	-1.00
Pulmonary function test, n (%)	4989 (39.7)	13566 (34.8)	10.00	4988 (39.7)	4943 (39.3)	0.70
Number of Pulmonologist visits, mean (SD)	1.1 (2.4)	1 (2.5)	3.50	1.1 (2.4)	1.1 (2.5)	0.90
Antibiotics, n (%)	9638 (76.6)	29724 (76.3)	0.80	9636 (76.6)	9601 (76.4)	0.70
Corticosteroids, n (%)	6750 (53.7)	18540 (47.6)	12.20	6748 (53.7)	6551 (52.1)	3.10
ICS (excluding Fluticasone), n (%)	3647 (29)	8369 (21.5)	17.40	3644 (29)	3386 (26.9)	4.60
LAMA, n (%)	884 (7)	3315 (8.5)	-5.50	884 (7)	883 (7)	0.00
LABA, n (%)	2532 (20.1)	12953 (33.2)	#####	2532 (20.1)	2143 (17)	8.00
Leukotriene receptor antagonist (excluding Montelukast), n (%)	93 (0.7)	150 (0.4)	4.70	91 (0.7)	68 (0.5)	2.30
SABA, n (%)	6687 (53.2)	21764 (55.9)	-5.40	6684 (53.2)	6657 (53)	0.40
SAMA, n (%)	656 (5.2)	2193 (5.6)	-1.80	656 (5.2)	629 (5)	1.00

9. Statistical analysis plans

Incidence rates for the outcome will be estimated for the treatment and reference groups before and after PS matching. The competing risk of death could be of concern for the current set of analyses if mortality is frequent among patients included in the cohort and if differences in the risk of mortality between treatment and reference groups are substantial. In the PS-matched sample, we will use cause-specific hazard models⁷ to provide hazard ratios averaged over the entire follow-up period as well as interval specific hazard ratios (1, 2, and 3 years) for the association between the treatment of interest and risk of ADRD after considering all-cause mortality as a competing event. Pre-specified subgroup analyses will be conducted based on age, sex, and baseline cardiovascular disease.

10. References

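### After matching, LABA (+8.0) and other ICS (+4.6) remain higher on montelukast by more than chance allows; the plan has no step that responds and names no adjustment

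*Combined protocol and SAP*

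**What the plan says.** Section 6b lists LABA, ICS other than fluticasone, and corticosteroids among the asthma treatment and severity covariates. Section 7 models treatment choice "conditional on baseline covariates using multivariable logistic regression constructed separately in each data source". It does not say whether interactions enter the model. Matching is 1:1 nearest neighbour with a caliper of 0.025 on the PS scale. Section 7 then states that estimates conditioned on the PS have no measured confounding. Balance is to be reported covariate by covariate as standardized differences, with no rule for what follows if a covariate stays unbalanced.

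Section 8 gives the result for the matched arms ("Montelukast (N = 12,572" and the same number on fluticasone). The matched entries are "2532 (20.1) 2143 (17) 8.00" for LABA, "3644 (29) 3386 (26.9) 4.60" for the row labelled "ICS (excluding Fluticasone), n", and "6748 (53.7) 6551 (52.1) 3.10" for the row labelled "Corticosteroids, n".

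Section 9 continues: "In the PS-matched sample, we will use cause-specific hazard models". It names no covariates for that model.

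**The concern.** LABA and ICS mark how intensively asthma was treated at baseline, and the plan itself lists them as treatment and severity indicators. If they still differ after matching, an unadjusted hazard ratio carries part of that difference.

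The direction for LABA is unusual. Loose matching leaves a residual with its original sign, which here would be LABA lower on montelukast. Instead the sign reversed. The pool was ample, since 12,572 of 12,575 montelukast initiators found a partner among 38,958 fluticasone initiators. This pattern points to how the PS was built or how the flag was defined, and the plan has no step that would respond to it.

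**Working it through.** **1. Reproduce the table.** Standardized difference = 100 x (p1 - p2) / sqrt{[p1(1 - p1) + p2(1 - p2)] / 2}. Counts are from section 8, with n = 12,572 per arm. If the PS balances a covariate, its chance SD is about 100 x sqrt(2/12,572) = 1.26.

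| Covariate | Matched counts | Printed | Recomputed | Chance SDs | Unmatched |
|---|---|---|---|---|---|
| LABA | 2,532 v 2,143 | 8.00 | 7.96 | 6.3 | -30.0 (printed as #####; from 2,532/12,575 v 12,953/38,958) |
| ICS, other | 3,644 v 3,386 | 4.60 | 4.57 | 3.6 | +17.4 |
| Corticosteroids | 6,748 v 6,551 | 3.10 | 3.14 | 2.5 | +12.2 |

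**2. Allow for the number of rows.** The table has 101 matched rows. The two-sided 5% Bonferroni bound is 3.48 chance SDs. LABA and ICS exceed it and corticosteroids does not. By chance, 101 x 2 x [1 - Phi(2.49)] = 1.3 rows would lie beyond 2.49. Next come asthma exacerbation (2.40, 1.9 SDs) and other leukotriene antagonists (2.31, 1.8 SDs), which are unremarkable.

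**3. Check that 1.26 is not too small.** The root mean square over all 101 rows is 1.09 chance SDs. Removing the three rows above leaves (101 x 1.088^2 - 6.31^2 - 3.63^2 - 2.49^2)/98 = (119.5 - 59.2)/98 = 0.615, whose square root is 0.78. The other rows are at least as tight as chance predicts.

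**4. Could a missing interaction do this?** Joint ICS/LABA counts are not in the documents, so this step rests on assumptions. Simulations used the section 8 ICS and LABA margins, the arm sizes, 1:1 matching and the 0.025 caliper. The PS had main effects only, and one further covariate was shifted between arms.

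| Assumed use of both, montelukast v fluticasone | Shift (SD) | LABA | ICS | ICS+LABA cell |
|---|---|---|---|---|
| 16.5% v 12% | 0.3 | +7 to +8 | about +4 | about +15 |
| 18% v 14% | 0.3 | about +7 | about +5 | about +12 |
| 17% v 10% | 0.1 | about +6.5 | about +5.5 | about +7 |
| 17% v 17% | 0.3 | +2 to +3 | about +2 | about +3 |
| 16.5% v 12% | 0 | 0 | 0 | 0 |

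Adding ICS x LABA brought all of these within about 1 of zero. A missing interaction can therefore produce the printed pattern. Whether it does, and how large the joint-cell imbalance is, depends on inputs the documents do not give.

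**5. Size of the bias.** For a covariate with hazard ratio h and a rare outcome, the bias factor is about [1 + p1(h - 1)] / [1 + p2(h - 1)]. No document gives h.

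- LABA alone, h = 1.5: (1 + 0.2014 x 0.5)/(1 + 0.1705 x 0.5) = 1.1007/1.0853 = 1.014. For h = 1.25 and h = 2.0 it is 1.007 and 1.026.
- High end, h = 1.5, joint cell 16.2% v 9.9% (a standardized difference of about 19): 1.081/1.0495 = 1.030. This ignores the offsetting shortfall in the LABA-only cell.

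**The case against.** The strongest reply is that every matched value is below 10, that the plan sets no stricter threshold, and that the effect on the hazard ratio is probably small. All of that stands, and it makes this a correctable weakness. It does not rescue the section 7 sentence, because the imbalance is in measured covariates and is too large for chance.

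A reader might infer that the table proves the PS model wrong. It does not. Section 7 neither includes nor excludes interactions, and the pattern appears in simulation only under some assumptions. Another explanation remains open. Section 6b removes fluticasone from the ICS row but puts no such limit on LABA. The assumed 16.5% v 12% leaves LABA without other ICS at 33.2 - 12 = 21.2% on fluticasone and 20.1 - 16.5 = 3.6% on montelukast. A gap like that could arise if the LABA part of a fluticasone combination product were counted. Section 5b requires no prior use of either study drug, so this needs a covariate window that includes the index date, or combination fills that are not treated as fluticasone use. The supplied text does not settle either, and the Appendix A code lists are not in it. The ICS residual does not separate the two explanations, since both work through the joint ICS/LABA pattern.

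A reader might also infer that the whole asthma-treatment block is out of balance. LAMA (0.0), SABA (0.4) and SAMA (1.0) are balanced, and corticosteroids is only suggestive. Finally, section 9 is silent on covariates; it does not rule adjustment out.

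**Conclusion.** The concern holds in a limited form. Two controller covariates, LABA and other ICS, remain imbalanced after matching beyond what chance explains. The plan nevertheless claims freedom from measured confounding, has no refit step and names no adjustment. This part rests only on the printed counts.

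The cause is not established. A missing ICS x LABA term is plausible, and so is a LABA flag that picks up the comparator product. A joint-cell imbalance above 10 is possible but not shown: simulations close to the printed LABA and ICS values gave about +7 to +15.

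At an assumed covariate hazard ratio of 1.5, the bias is about 1.4% through LABA alone and about 3% at the high end. It would be systematic and would not shrink with sample size. If the covariate raises dementia risk, it works against montelukast. The documents also do not say which of analyses 1 to 4 the section 8 table describes.

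**What to change.** Before outcomes are analysed:

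1. Check whether the baseline LABA flag counts the index fluticasone combination product, and state the covariate window. If it does count it, correct the flag before using it in any model.
2. Tabulate none, ICS only, LABA only and ICS+LABA by arm, before and after matching.
3. In section 7, add the ICS x LABA term, refit, re-match and report the four cells in section 8.
4. In section 9, include LABA and ICS as covariates in the cause-specific hazard model, or as a sensitivity analysis if re-matching restores balance.
5. Reword section 7 to say that matching aims to reduce measured confounding, subject to the balance shown.

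No general numerical trigger for adjustment is proposed. A cut-off of two chance SDs would flag about 5 of 101 rows by chance.

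The cost is SAP wording plus one refit and re-match on data already held. In simulations near the printed values almost no pairs were lost. In one extreme scenario (18% v 5% joint use), 12,205 pairs remained.

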Data Analysis for Drug Repurposing for Effective Alzheimer's Medicines – Montelukast vs Fluticasone

NCT05457855

July 10, 2023

1. Comparison Details

a. Intended aim(s)

To evaluate the comparative risk of dementia onset between patients treated with Montelukast versus Fluticasone for asthma.

b. Primary endpoint

Incident dementia (i.e., Alzheimer's disease, vascular dementia, senile, presenile, or unspecified dementia, or dementia in other diseases classified elsewhere).

[figure not shown]
2. Person responsible for implementation

[figure not shown]
[name]

3. Data Source(s)

Medicare, 2008-2018

4. Study Design Diagrams

5. Cohort Identification

a. Cohort Summary

This study will employ a new user, active comparator, observational cohort study design comparing Montelukast versus Fluticasone. The patients will be required to have continuous enrollment during the baseline period of 365 days before initiation of study drugs (cohort entry/index date). Follow-up for the outcome (dementia) differs between analyses. Follow-up begins the day after drug initiation (analysis 1, 3, 4); 180 days after drug initiation (analysis 2).

b. Key details regarding cohort creation

Index date:

- Day of initiation of new Montelukast versus Fluticasone use

Inclusion criteria for analyses 1, 3, 4:

- Aged \geq 65 years on the index date
- 365 days enrollment in Medicare Parts A, B, and D with no HMO coverage
- No use of Montelukast versus Fluticasone, any time prior to index date (all available lookback approach with a minimum of 365 days)
- No diagnosis of dementia any time prior to and including index date
- No history of nursing home admission recorded in any time prior to and including index date
- At least two claims with asthma diagnosis recorded in 365 days prior to index date (ICD-9 493.0x, 493.1, 493.2x, 493.8x, 493.9x or ICD-10 J44.0, J44.1, J44.9, J45.2x, J45.3x, J45.4x, J45.5x, J45.9x)

Inclusion criteria for analysis 2:

- Aged \geq 65 years on the index date
- 365 days enrollment in Medicare Parts A, B, and D with no HMO coverage or 365 days registration with a practice contributing data to CPRD prior to index date
- No use of Montelukast versus Fluticasone, any time prior to index date (all available lookback approach with a minimum of 365 days)
- No diagnosis of dementia any time prior to and including index date
- No history of nursing home admission recorded in any time prior to and including index date

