Antidepressants	3634 (28.9)	11842 (30.4)	-3.30	3634 (28.9)	3557 (28.3)	1.40
Angiotensin converting enzyme inhibitors (ACEi)	3269 (26)	10938 (28.1)	-4.70	3268 (26)	3300 (26.2)	-0.60
Angiotensin II receptor blockers (ARBs)	3599 (28.6)	10554 (27.1)	3.40	3598 (28.6)	3563 (28.3)	0.60
Beta blockers	4312 (34.3)	14499 (37.2)	-6.10	4312 (34.3)	4274 (34)	0.60
Calcium channel blockers	3182 (25.3)	10328 (26.5)	-2.80	3181 (25.3)	3192 (25.4)	-0.20
Disease-modifying antirheumatic drugs (DMARDs)	457 (3.6)	1522 (3.9)	-1.40	457 (3.6)	452 (3.6)	0.20
Diuretics	5260 (41.8)	17028 (43.7)	-3.80	5259 (41.8)	5306 (42.2)	-0.80
Biologics (Omalizumab, Mepolizumab, Reslizumab, Benralizumab, Dupilumab)	89 (0.7)	218 (0.6)	1.90	89 (0.7)	77 (0.6)	1.20
Comorbid conditions, n (%)						
Atrial fibrillation	1527 (12.1)	5492 (14.1)	-5.80	1527 (12.1)	1543 (12.3)	-0.40
Heart failure	1397 (11.1)	5145 (13.2)	-6.40	1397 (11.1)	1352 (10.8)	1.10
Stroke or transient ischemic attack	858 (6.8)	3209 (8.2)	-5.40	858 (6.8)	867 (6.9)	-0.30
Peripheral vascular disease	1056 (8.4)	3915 (10)	-5.70	1055 (8.4)	1055 (8.4)	0.00
Hyperlipidemia	8900 (70.8)	27637 (70.9)	-0.40	8898 (70.8)	8820 (70.2)	1.40
Renal dysfunction	1706 (13.6)	6279 (16.1)	-7.20	1705 (13.6)	1704 (13.6)	0.00
Chronic liver disease	810 (6.4)	2628 (6.7)	-1.20	809 (6.4)	807 (6.4)	0.10
Ischemic heart disease	3250 (25.8)	11107 (28.5)	-6.00	3250 (25.9)	3170 (25.2)	1.50
Chronic obstructive pulmonary disease	5222 (41.5)	16890 (43.4)	-3.70	5220 (41.5)	5213 (41.5)	0.10
Malignancy	3369 (26.8)	11073 (28.4)	-3.70	3369 (26.8)	3411 (27.1)	-0.80
Drug or alcohol abuse or dependence	944 (7.5)	4336 (11.1)	#####	944 (7.5)	936 (7.4)	0.20
Venous thromboembolism	425 (3.4)	1565 (4)	-3.40	425 (3.4)	423 (3.4)	0.10
Rheumatoid Arthritis	595 (4.7)	1994 (5.1)	-1.80	595 (4.7)	592 (4.7)	0.10

DREAM study protocol - Comparison 10 Montelukast vs Fluticasone

Other Asthma treatments and Asthma severity indicators						
Asthma exacerbation, n (%)	213 (1.7)	478 (1.2)	3.90	211 (1.7)	174 (1.4)	2.40
Bronchiectasis, n (%)	347 (2.8)	1006 (2.6)	1.10	346 (2.8)	357 (2.8)	-0.50
Interstitial lung disease, lung fibrosis, ARDS, n (%)	1220 (9.7)	3941 (10.1)	-1.40	1219 (9.7)	1205 (9.6)	0.40
Lung Cancer, n (%)	144 (1.1)	674 (1.7)	-4.90	144 (1.1)	137 (1.1)	0.50
Pneumonia, n (%)	694 (5.5)	2455 (6.3)	-3.30	693 (5.5)	670 (5.3)	0.80
Pulmonary Hypertension, n (%)	194 (1.5)	691 (1.8)	-1.80	194 (1.5)	182 (1.4)	0.80
Respiratory failure, n (%)	723 (5.7)	2725 (7)	-5.10	722 (5.7)	704 (5.6)	0.60

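### The LABA covariate lacks the study-drug exclusion that the ICS and leukotriene antagonist covariates carry, and the balance table suggests, without proving, that index-day fluticasone/LABA fills are counted in it

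*Combined protocol and SAP*

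**What the plan says.** Section 6b lists LABA among the asthma treatments and severity indicators that enter the propensity score (PS). Two neighbouring covariates leave out the study drug of their class: "ICS (excluding Fluticasone), n" in the Section 8 table, and leukotriene receptor antagonists other than montelukast. LABA carries no exclusion.

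The new-user rule in Section 5b reads "No use of Montelukast versus Fluticasone, any time prior to index date". Section 5a requires "continuous enrollment during the baseline period of 365 days before initiation of study drugs", and Section 7 builds the PS on baseline covariates by logistic regression. Section 7 then states: "Pair matching will be conducted using a nearest-neighbor algorithm", with a caliper of 0.025 on the PS scale.

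The readable text does not say whether drug covariates include the index day, or whether fluticasone includes fluticasone/LABA combination products. The design diagrams (Section 4) and the code lists (Appendix A) may say so, but they are not in the supplied text.

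**The concern.** No cohort member may have used fluticasone before the index date. If that rule covers every fluticasone product, any baseline LABA taken together with an ICS should also appear in the non-fluticasone ICS row. In the montelukast group ICS exceeds LABA, as expected. In the fluticasone group LABA exceeds ICS by a wide margin. One explanation is that a fluticasone/LABA product dispensed on the index day is scored as baseline LABA.

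If so, part of the exposure sits in the PS as if it were a confounder. Matching would then select comparators partly by which fluticasone product they started, and the LABA line of the balance table would not describe pre-index treatment.

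**Working it through.** **Inputs** (Section 8 table)

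| | Montelukast | Fluticasone |
|---|---|---|
| Unmatched N | 12,575 | 38,958 |
| LABA, unmatched | 2,532 (20.1%) | 12,953 (33.2%) |
| Non-fluticasone ICS, unmatched | 3,647 (29.0%) | 8,369 (21.5%) |
| Matched N | 12,572 | 12,572 |
| LABA, matched | 2,532 (20.1%) | 2,143 (17%) |
| Non-fluticasone ICS, matched | 3,644 (29.0%) | 3,386 (26.9%) |

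**1. Reproduce the table.** Standardized difference = 100 × (p1 − p0) / √{[p1(1 − p1) + p0(1 − p0)] / 2}.
- LABA matched: 7.96 (printed 8.00). ICS: 17.38 unmatched and 4.57 matched (printed 17.40 and 4.60). The formula reproduces the printed values.
- LABA unmatched prints as hash marks. It recomputes to -29.98.
- After matching, +8.0 is the largest residual in the table. ICS at 4.6 is next.

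**2. LABA without another ICS.** The number with LABA but no non-fluticasone ICS is at least LABA − ICS.
- Fluticasone: 12,953 − 8,369 = 4,584, which is 11.8% of 38,958 and 35.4% of 12,953. LAMA users number 3,315, so at least 4,584 − 3,315 = 1,269 of these have no LAMA either.
- Montelukast: 2,532 − 3,647 = -1,115, so no such excess is forced.
- LABA/ICS ratio: montelukast 2,532/3,647 = 0.69; fluticasone 12,953/8,369 = 1.55 before matching and 2,143/3,386 = 0.63 after.

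**3. Who is removed by matching.**
- LABA-coded fluticasone starters: 12,953 − 2,143 = 10,810 removed (83.5%).
- Others: 38,958 − 12,953 = 26,005, of whom 12,572 − 2,143 = 10,429 are kept and 15,576 removed (59.9%).
- Benchmarks: 1:1 matching removes 67.7% of all fluticasone starters (1 − 12,572/38,958). Perfect LABA balance would remove 80.5% of the LABA-coded ones (1 − 2,532/12,953).

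**4. How many could be index-day only.** The documents give no direct count, so this is a range by assumption about true pre-index LABA in the fluticasone group.

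| Assumption | Pre-index LABA | Index-day only | Unmatched difference |
|---|---|---|---|
| No index-day counting | 12,953 (33.2%) | 0 | -30.0 |
| No more common than other ICS | 8,369 (21.5%) | 4,584 | -3.3 |
| Same prevalence as montelukast | 7,844 (20.1%) | 5,109 | 0 |
| Same LABA/ICS ratio as montelukast | 5,810 (14.9%) | 7,143 | +13.8 |

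**5. Effect on the matched balance.** Suppose 35.4% of the 2,143 matched LABA-coded fluticasone users were index-day only and the montelukast count did not change. Then 2,143 × (1 − 0.354) ≈ 1,384 (11.0%) stand against 20.1%, a standardized difference of about 25. With 0% it stays at 8.

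**6. Can the table identify the cause?** An illustrative simulation used ICS, LABA and one further covariate, a main-effects logistic PS, 1:1 nearest-neighbor matching and a 0.025 caliper.

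| Scenario for fluticasone starters | Matched LABA | LABA difference | ICS difference | LABA-coded kept |
|---|---|---|---|---|
| Index-day LABA added | 17.5% | 7.3 | 5.7 | 16.6% |
| No index-day LABA; extra LABA mostly outside ICS | 16.6% | 7.7 | 5.2 | 16.2% |
| No index-day LABA; LABA higher with and without ICS | 20.9% | 0.8 | 0.7 | 19.2% |
| Observed | 17% | 8.0 | 4.6 | 16.5% |

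The first two scenarios are practically indistinguishable, so the overshoot and the differential removal do not separate them.

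**The case against.** The strongest case is that the text points away from index-day counting. Section 5a places baseline before initiation, and the PS uses baseline covariates. The material that would settle the matter is not in the supplied text, and that is not a fault of the plan. The documents never mention a fluticasone/LABA product. All of this stands, although the Section 5a phrase describes enrollment rather than the drug-covariate window, and the dementia and nursing home exclusions do take in the index date.

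Second, LABA without ICS in COPD may be real. The "Chronic obstructive pulmonary disease" row shows 16,890 fluticasone starters, and 4,584 is 27% of them. The inclusion codes admit J44 diagnoses. Smoking (27.3% vs 22.3%), oxygen use (2.8% vs 2.1%) and respiratory failure (7.0% vs 5.7%) run higher in that arm. Similar COPD (43.4% vs 41.5%) and LAMA (8.5% vs 7.0%) prevalence makes this explanation less likely but does not rule it out.

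Third, fluticasone may mean the single-ingredient product only, so that earlier combination users enter as new users. That should also have pushed LABA above ICS in montelukast starters, which is not seen. If it were the case, the new-user rule would itself need attention.

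On the other side, a strictly pre-index window under the new-user rule would make the ICS and leukotriene exclusions redundant. Their presence fits index-day counting, though it may be mere caution.

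A reader might infer three stronger things. One is that the PS demonstrably conditions on the comparator drug; the table cannot show that. Another is that 4,584 is the minimum number miscoded; it is the minimum with LABA and no other ICS, and the minimum miscoded is zero. The third is that matching wrongly strips out LABA users or leaves them without counterparts. But perfect balance would already remove 80.5%, the shortfall against it is 2,532 − 2,143 = 389 people, and all 2,532 LABA-coded montelukast starters stay in the matched set.

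**Conclusion.** The missing exclusion on LABA is a fact of the documents, as are the reversed LABA/ICS pattern and the +8.0 matched residual. Index-day counting of a fluticasone/LABA product is a likely explanation but not an established one. It rests on two assumptions: that fluticasone includes such products, and that the covariate window reaches the index day. The number affected could range from 0 to about 7,100; the upper figure borrows montelukast's LABA/ICS ratio and is not a bound.

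If index fills are counted, the matched fluticasone group has less pre-index LABA than printed. The true difference then exceeds 8, reaching about 25 under the 35.4% assumption. No effect on the hazard ratio, in size or direction, can be derived from the documents. The clarification should be made before the outcome analysis, and the residual LABA difference needs comment whatever the cause.

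**What to change.** - In Section 6b, define LABA, like ICS and leukotriene antagonists, to exclude dispensings of the study drug, meaning any fluticasone-containing product. State that drug covariates are measured strictly before the index date.
- State whether fluticasone as a study drug includes combination products.
- Cross-tabulate LABA by non-fluticasone ICS by arm, with and without the index day.
- If the LABA counts change, re-estimate the PS, re-match and re-issue the balance table before the outcome analysis. If they do not, keep the match and comment on the +8.0.

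The cost is a few lines of text and a covariate re-pull. The matched set and the table may change. Separate hazard ratios for single-agent and combination starters would be informative but are optional.
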